4.6 Destruction and Return of Study Drug

4.6.1 Destruction of Study Drug

If study drugs (those supplied by the sponsor or sourced by the investigator) are to be destroyed on site, it is the investigator's responsibility to ensure that arrangements have been made for the disposal, procedures for proper disposal have been established according to applicable regulations, guidelines and institutional procedures, and appropriate records of the disposal have been documented. The unused study drugs can only be destroyed after being inspected and reconciled by the responsible BMS Study Monitor.

4.6.2 Return of Study Drug

Upon completion or termination of the study, all unused and/or partially used study drug that was supplied by the sponsor must be returned to BMS.

All study drug returned to BMS must be accompanied by the appropriate documentation and be clearly identified by protocol number and study site number on the outermost shipping container. Returned supplies should be in the original containers (eg, patient kits that have clinical labels attached). Empty containers should not be returned to BMS. It is the investigator's responsibility to arrange for disposal of all empty containers, provided

Saxagliptin and Dapagliflozin	CV181169
and	Clinical Protocol

that procedures for proper disposal have been established according to applicable federal, state, local, and institutional guidelines and procedures, and provided that appropriate records of disposal are kept. The return of unused study drug, those that were supplied by the sponsor, should be arranged by the responsible Study Monitor.

Saxagliptin and Dapagliflozin

and

CV181169 Clinical Protocol

5 STUDY ASSESSMENTS AND PROCEDURES

5.1 Flow Chart/Time and Events Schedule

Table 5.1:Flow Chart for CV181169											
Procedure	Screening Period	Lead- In Period			Dou		nd Treatment Pe vindow ± 5days		Notes		
	WK (-6)WK (-4)Day 1WK 6WK 12WK 18WK S Term							Rescue / Early Treatment Discontinuation			
Eligibility Assessments											
Obtain Informed Consent	Х										
Review Medical History	Х										
Review Eligibility Criteria	Х										
Review Randomization Criteria			X								

Table 5.1:									
Procedure	Screening Period	Lead- In Period	Notes						
	WK (-6)	WK (-4)	Day 1	WK 6	WK 12	WK 18	WK 24/ Study Termination	Rescue / Early Treatment Discontinuation	
General Procedures									
Brief Physical Examination		X	Х	Х	Х	Х			
Complete Physical Examination	Х						Х	Х	
Body Weight	Х	X	Х	Х	Х	Х	Х	Х	
Seated Blood Pressure and Heart Rate	Х		X	X	Х	X	Х	Х	
Height	Х								
Body Mass Index (BMI)	Х								
Waist Circumference	Х		Х				Х		
12-Lead ECG			X				X*	X*	* Only 2 ECGs performed/subject. ECG is not required at Wk 24 if subject has been rescued or discontinued from treatment prior to Week 24

Saxagliptin and Dapagliflozin and

CV181169 Clinical Protocol

Saxagliptin	and	Dapagliflozin	

and

Table 5.1:	Flow Chart	for CV1	81169						
Procedure	Screening Period	Lead- In Period			Dou	ble-Blin Visit v	Notes		
		WK (-4)	Day 1	WK 6	WK 12	WK 18	WK 24/ Study Termination	Rescue / Early Treatment Discontinuation	
Review Concomitant Medications / Procedures	X	X	X	X	X	X	Х	Х	
Contact IVR system	X	X	X	X	X	X	X*	X**	* Call to register study termination only **Call at Rescue/ETD visit only if drug re-supply required.
Provide Diet and Exercise Counseling	Х	Х	Х	Х	X	X		Х	
Provide Glucose Meter and Supplies / Instructions		X	X	Х	Х	Х		X*	*Only if required
Provide logs / Instructions		Х	Х	Х	Х	Х			
Review study logs			Х	Х	Х	Х	Х	Х	

Table 5.1:									
Procedure	Screening Period	Lead- In Period			Dou	ble-Bli Visit v	Notes		
	WK (-6)	WK (-4)	Day 1	WK 6	WK 12	WK 18	WK 24/ Study Termination	Rescue / Early Treatment Discontinuation	
Safety Assessment									
Assess Adverse Events, Hypoglycemia Episodes		X	X	X	X	X	Х	X	
Central Laboratory			•		•				
Pregnancy Test (urine) WOCBP only	Х	X	X	X	X	X	X	X	Home pregnancy test kits sent home with WOCBP to perform pregnancy tests between visits and record resul in log book
Blood & Urine Standard Safety Laboratory Panels	Х	X	X	Х	Х	Х	Х	Х	
Dipstick Urinalysis (local)	Х	X							Positive dipstick at Wk-4 will require repeat test with microscopy prior to randomization. (See Appendix 3)
Microscopic Urinalysis	Х	X*			X		Х	X	*Microscopic urinalysis only performed at Wk-4 if dipstick resul is positive. (See Appendix 3)

Date:

Saxagliptin	and D	apagliflozin

and

Table 5.1:	Flow Chart for CV181169													
Procedure	Screening Period	Lead- In Period			Dou	ble-Blir Visit v	Notes							
	WK (-6)	WK (-4)	Day 1	WK 6	WK 12	WK 18	WK 24/ Study Termination	Rescue / Early Treatment Discontinuation						
Spot Urine Glucose Quantification and glucose:creatinine ratio			Х		Х		X	Х						
HbA1C	Х	X	Х	Х	Х	Х	X	Х						
FPG	X	X*	X	X	Х	Х	Х	Х	*FPG must be >270 mg/dL. See section 3.3.1 for more details.					
Assess FPG for Rescue				Х	Х	Х		X						
Fasting C-Peptide	Х													
MTT (Glucose, insulin, C-peptide, glucagon)			X				X*	X*	Subject must be fasted for at least 8 hrs prior to the MTT Subject must abstain from tobacco, alcohol and caffeine for at least 8 hr prior to the MTT					
									*Maximum of 2 MTTs performed/subject. MTT not conducted at Wk24 if subject has been rescued or discontinued from treatment prior to Wk 24.					

Saxagliptin	and Dapagliflozin	

and

Table 5.1:									
Procedure	Screening Period	Lead- In Period			Dou	ble-Blir Visit v	Notes		
	WK (-6)	WK (-4)	Day 1	WK 6	WK 12	WK 18	WK 24/ Study Termination	Rescue / Early Treatment Discontinuation	
eGFR (MDRD) & Serum Creatinine (SCr)	Х		X	X	X	X	Х	Х	
Fasting Serum Lipids (Total-C, LDL-C, HDL- C, TG)			X				Х	X	
Hepatitis Screen Panel, TSH	Х	Х							
SDF-1 biomarker			X				Х	Х	
Drug Dispensing			•		•	•			
Dispense Study Medication		X*	X	X	X	X		X	*Only metformin XR dispensed at week -4.
Dispense, open-label rescue medication, as needed (if applicable				Х	Х	Х		Х	
Review Study Medication Compliance			Х	Х	Х	Х	Х	Х	

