3.3.1 Inclusion Criteria

1) Signed Written Informed Consent

a) Subjects must be willing and able to give signed and dated written informed consent.

2) Target Population

a) Subjects with T2DM with inadequate glycemic control, defined as a central laboratory HbA1c \ge 8.0 and \le 12.0 % obtained at the screening visit.

Note: At Week -4 a qualification check will be performed and subjects will be excluded, if their FPG is > 270 mg/dl. A re-test will be permitted within 7 days if the initial result was > 270mg/dl but < 300mg/dl. Subjects will be excluded if the mean value of the Week -4 result and the re-test result is > 270mg/dl.

- b) Stable metformin therapy for at least 8 weeks prior to screening at a dose ≥ 1500 mg per day.
- c) C-peptide $\geq 1.0 \text{ ng/mL} (0.34 \text{ nmol/L})$ at screening visit
- d) BMI $\leq 45.0 \text{ kg/m}^2$ at the screening visit

3) Age and Reproductive Status

- a) Men and women, aged ≥ 18 years old at time of screening visit.
- b) Women of childbearing potential (WOCBP) must be using an acceptable method of contraception to avoid pregnancy throughout the study in such a manner that

the risk of pregnancy is minimized. See Section 3.3.3 for the definition of WOCBP.

- c) WOCBP must have a negative serum or urine pregnancy test (minimum sensitivity 25 IU/L or equivalent units of HCG) within 24 hours prior to the start of investigational product.
- d) Women must not be breastfeeding.
- e) Sexually active fertile men must use effective birth control if their partners are WOCBP.

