3.3.2.1 Randomization Criteria

Exclusion:

• FPG >270mg/dl as measured at Week -4

Note: At Week -4 a qualification check will be performed and subjects will be excluded, if their FPG is > 270 mg/dl. A re-test will be permitted within 7 days if the initial result was > 270 mg/dl but < 300mg/dl. Subjects will be excluded if the mean value of the Week -4 result and the re-test result is > 270 mg/dl.

Eligibility criteria for this study have been carefully considered to ensure the safety of the study subjects and to ensure that the results of the study can be used. It is imperative that subjects fully meet all eligibility criteria.

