3.5.1.1 Initiation of Rescue Medication

Pre-specified glycemic criteria (see Table 3.5.1.1), based upon central laboratory FPG and repeat, confirmatory FPG, have been established during the double-blind treatment period, starting at Week 6, and up to Week 24 visits, to determine eligibility for open label rescue medication.

Table 3.5.1.1:	Lack of Glycemic Control Criteria for Initiation of Rescue Medication		
Visit Label		Central Laboratory FPG	
Week 6		FPG > 270 mg/dL (15.0 mmol/L)	
After Week 6 to Week 12 (excluding Week 12)FPG > 240 mg/dL (13.3 mmol/L)		FPG > 240 mg/dL (13.3 mmol/L)	
Week 12 to Week 24 FPG > 200 mg/dL (11.1 mmol/L)		FPG > 200 mg/dL (11.1 mmol/L)	

Subjects with a central laboratory FPG value meeting the lack of glycemic control criterion at a pre-specified visit will be scheduled for a follow-up visit (within 3 - 5 days) to obtain a second central laboratory FPG value and review the subject's glucose meter readings. If the repeat central laboratory FPG value still meets the criterion, the subject must be rescued.

Subjects who meet rescue criteria in the double-blind treatment period must first complete the Rescue Visit procedures before receiving open-label rescue medication to ensure that important trial endpoint measurements are collected. (See Section 5.8.3.1) Following completion of the Rescue Visit, rescued subjects will be given open-label antidiabetic rescue medication (Insulin or other antidiabetic agents except GLP-1 analogs, other DPP4/SGLT2 inhibitors or metformin) to be initiated at the lowest starting dose and titrated in accordance with the approved product label in the applicable country at the discretion of the investigator, in addition to their double-blinded study medication. Rescued subjects will then continue in the double-blind treatment period according to their original visit schedule.

Note: Rescue medication will not be provided by Sponsor in this study.

Following initiation of open-label rescue antidiabetic medication, rescued subjects should be scheduled for titration visits to increase their antidiabetic medication dose, as tolerated and in accordance with the approved product label for that country and by their glycemic response and as per the Investigator's judgment.

3.5.2 Discontinuation Guidelines due to Protocol-Defined Major Hypoglycemia Episode or Recurrent Non-Major Hypoglycemia Episodes

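### The Table 5.1 note on the Week -4 FPG states the 270 mg/dL threshold in the opposite direction to the exclusion rule in the section it cites

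*Protocol*

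**What the plan says.** The Week -4 FPG threshold appears in four places in the protocol.

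- **Section 5.1, Table 5.1, FPG row.** The asterisk sits on the Week -4 cell, and its note reads "FPG must be >270 mg/dL. See section 3.3.1 for more details".
- **Section 3.3.1, note to the target-population criterion.** "At Week -4 a qualification check will be performed and subjects will be excluded, if their FPG is > 270 mg/dl". It goes on: "A re-test will be permitted within 7 days if the initial result was > 270mg/dl but < 300mg/dl". The decision after a re-test is: "Subjects will be excluded if the mean value of the Week -4 result and the re-test result is > 270mg/dl".
- **Section 3.3.2.1, Randomization Criteria.** Under the exclusion label it lists "FPG >270mg/dl as measured at Week -4" and repeats the re-test and mean-value provisions.
- **Synopsis, Randomization Criteria.** It gives the same exclusion and the same re-test note as Section 3.3.2.1.

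Table 5.1 also has a row for reviewing eligibility criteria, marked at Week -6 only, and a row for reviewing randomization criteria, marked at Day 1 only.

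**The concern.** The note phrases as a requirement what three other places phrase as a ground for exclusion, and one of those places is the section it names as its source. Both cannot be followed: a subject who meets the note on a single value fails Section 3.3.2.1, and a subject who satisfies Section 3.3.2.1 on a single value fails the note.

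The location matters. Table 5.1 is the schedule that sites follow visit by visit. At Week -4, when the FPG check is made, neither criteria-review row is marked, so the note is the schedule's only statement of the threshold at that visit. It also leaves out the re-test, which must take place within 7 days. A site that misreads the threshold at Week -4 and discovers this at Day 1, four weeks later, will find the re-test window closed.

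At stake are correct admission to randomization and avoidable eligibility deviations. Section 3.3.2.1 itself stresses that subjects must fully meet the eligibility criteria.

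**Working it through.** No figure in the plan has to be reproduced, because the point concerns the direction of an inequality. The check is to write each rule out and apply both to the same values.

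**Rule A (Sections 3.3.1 and 3.3.2.1, synopsis).** Let *f* be the Week -4 FPG and *r* the re-test, both in mg/dL.
- *f* ≤ 270: not excluded.
- 270 < *f* < 300: a re-test is permitted; excluded if (*f* + *r*)/2 > 270.
- *f* ≥ 300: excluded, with no re-test.

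**Rule B (Table 5.1 note, read literally and alone).**
- *f* > 270: passes.
- *f* ≤ 270: does not pass.

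Illustrative values, chosen to cover each branch:

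| First FPG | Re-test | Mean | Rule A | Rule B |
|---|---|---|---|---|
| 150 | – | – | passes | fails |
| 200 | – | – | passes | fails |
| 270 | – | – | passes | fails |
| 271 | none done | – | excluded | passes |
| 285 | 250 | (285 + 250)/2 = 267.5 | passes | passes |
| 285 | 260 | (285 + 260)/2 = 272.5 | excluded | passes |
| 300 | – | – | excluded | passes |
| 320 | – | – | excluded | passes |

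The rules agree in one branch only: 270 < *f* < 300 with (*f* + *r*)/2 ≤ 270, that is, *r* ≤ 540 − *f*. For *f* = 285 this needs *r* ≤ 255. In every other branch they give opposite answers.

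**Could the sign be a conversion error in the text?** This cannot be fully ruled out from extracted text. However, other inequality signs in the protocol are preserved, including the same threshold in the synopsis and Sections 3.3.1 and 3.3.2.1. Nothing suggests a misread sign here.

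**Does any design figure depend on it?** Section 8.1 derives 163 subjects per group and 516 randomized from an HbA1c difference of 0.4%, a standard deviation of 1.0%, a two-sided 0.05 level for both comparisons and 5% of subjects without a post-baseline assessment. The FPG threshold enters none of these.

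**The case against.** The best defence is that this is a slip in a single table note and that the protocol contains its own corrections. The note sends the reader to Section 3.3.1, where the full rule stands. The rule is stated consistently in three places. The schedule calls for a review of randomization criteria on Day 1, and the section of that name excludes Week -4 FPG above 270 mg/dL. Read literally, the note would also disqualify every subject at or below 270 mg/dL, which is odd enough that sites would probably query it early.

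This defence stands as far as likelihood goes. A reader might infer that sites working from the flow chart would randomize exactly the subjects whom the protocol excludes. The documents do not support that. It would need a site to pass over both the cross-reference and the Day 1 review, and some subjects with a re-test pass under both rules.

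A second tempting inference is that subjects admitted under the note would start treatment above the Week 6 rescue threshold, which is also 270 mg/dL (Table 3.5.1.1), and so raise rescue and remove HbA1c values from the primary analysis. That does not follow either. The value known to exceed 270 mg/dL is the one from Week -4. A four-week metformin XR lead-in with diet and exercise counseling comes next, and FPG is measured again on Day 1. Rescue at Week 6 then depends on a new central-laboratory value and a confirmatory repeat, after six weeks of active add-on treatment in every arm. More rescue is conceivable, but the protocol gives no basis for a size. The check also precedes randomization, so nothing here shows a bias between arms.

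What the defence does not do is make the note correct. A site that complies with it breaches Section 3.3.2.1.

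**Conclusion.** The contradiction is real and should be corrected. One note in the visit schedule reverses the direction of a randomization threshold that the synopsis, Section 3.3.1 and Section 3.3.2.1 state consistently. Applied alone, it could pass subjects whom those sections exclude and would turn away every subject at or below 270 mg/dL. The only overlap is a first value above 270 and below 300 mg/dL with a two-test mean of 270 mg/dL or less.

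The size is that of an eligibility inconsistency in an operational table. How many subjects it might affect cannot be estimated from the protocol, and the cross-reference and Day 1 review lower the chance that it affects any. Alpha, power and sample size are untouched. The conclusion assumes that the inequality sign in the note is as printed. It does not rest on any effect on rescue rates or on the primary analysis, nor on the interactive voice response system testing FPG, a function that Section 4.2 does not describe.

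**What to change.** Reconcile the Table 5.1 note with Sections 3.3.1 and 3.3.2.1 so that the Week -4 FPG threshold, its direction, the re-test window and the mean-value rule read the same wherever they appear. Cite Section 3.3.2.1 in the note alongside Section 3.3.1. Confirm that any site or system material derived from the flow chart carries the reconciled rule.

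The cost is a one-line protocol correction and a check of derived materials. The design, analysis and sample size stay as they are.

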5.2 Study Materials

BMS will supply the sites with the following materials:

- Blood glucose meters. One meter will be provided to each study subject at screening and one additional meter will be provided to each investigative site
- Blood glucose test strips
- Lancets
- Glucose control solutions
- Subjects logs for hypoglycemia episodes or events suggestive of hypoglycemia episodes reporting, as well as daily medication logs and pregnancy testing logs
- Electronic Case Report Forms (eCRFs).
- Patient education material and Site Support Tools
- Liquid Meal for Liquid Meal Tolerance Test (MTT)
- Study Drug logs
- Home pregnancy test kits

The central laboratory will provide all laboratory-related materials to the study site.

5.3 Safety Assessments

Safety Assessments will include adverse event reporting as well as marked abnormalities in clinical laboratory tests. Please refer to Appendix 2 for details on central laboratory assessments.

The procedures described in the sections that follow will also be completed to ensure subject's safety.

5.3.1 Self-Monitoring of Blood Glucose (SMBG)

Glucose meters will be supplied to each study site. Subjects will receive a glucose meter, supplies and instruction on their use. Supplies will be provided to allow for approximately 60 blood glucose assessments per month for the duration of the study. The Investigator may require more frequent readings based on local clinical practice. Subjects should bring their glucose meter with them to each study visit to ensure that it is functioning properly. Subjects may keep the glucose meters at the end of the study.

The Sponsor recommends instructing the subjects to self-monitor their blood glucose at least one time per day, and in the occurrence of hypoglycemic symptoms, and to contact the Investigator in the event of an unusually high or low blood glucose value. In addition, study subjects should comply with site's instructions with regard to self-monitoring of blood glucose and should promptly report to the site blood glucose values and/or signs and symptoms suggestive of a hypoglycemia episode.

The memory of the glucose meter should be reviewed to compare with the subject's hypoglycemia episode log, as applicable. The glucose values should be reviewed by the site to identify any unusual high or low values, and to confirm that the values (from the glucose meter's memory and/or from the subject's hypoglycemia log) were obtained for the subject. If fingerstick glucose values are discordant from glycemic control assessed by the central laboratory or with clinical symptoms, the subject's glucose meter should be tested and the procedure for using it reviewed with the subject.

5.3.1.1 Guidance on Management and Reporting of Hypoglycemia Episodes

Hypoglycemia may be an expected event in subjects who are treated for diabetes. Subjects and their family members must be aware of the possibility that hypoglycemia may occur and the dangers associated with low blood sugar.

Study subjects must be properly instructed on the recognition and management of hypoglycemia. Subjects should record in their logs any hypoglycemic symptoms. They should be encouraged to measure, when possible, their blood glucose values when they have symptoms of hypoglycemia. Subjects should carry with them easily ingestible forms of carbohydrate at all times in order to treat an event of hypoglycemia should it occur.

During clinical trials, subjects frequently report symptoms of hypoglycemia when asked, even when treated with placebo or medications not otherwise associated with hypoglycemia. As hypoglycemia is an important event associated with diabetes therapy, all episodes which could be consistent with the clinical definition of hypoglycemia **as assessed by the Investigator** should be documented and reported on the appropriate eCRF page.

Hypoglycemia eCRF pages will be used to document all reported episodes of hypoglycemia. The Investigator is responsible for questioning the subject about all symptoms reported on the hypoglycemia log and for determining if they meet the

clinical definition of hypoglycemia. Only symptoms and/or blood glucose values deemed by the Investigator to meet the definition of hypoglycemia should be reported on the hypoglycemia eCRF pages. Signs and symptoms of hypoglycemia, hypoglycemia episode or discontinuation due to hypoglycemia should not be reported on the AE eCRF page, unless the event fulfills protocol criteria for a Serious Adverse Event (see Section 6.1.1), in which case an SAE form must be completed in addition to the hypoglycemia eCRF pages for hypoglycemia.

5.3.2 Guidance on Assessment of Urinary Infections & Hematuria

5.3.2.1 Guidance on Assessment of Urinary Infections

The following is presented to assist in the classification and management of urinary tract infections. It is not intended to supplant investigators' clinical judgment:

Study drug should be withheld in subjects with clinical evidence of upper tract UTI (eg pyelonephritis) or presumed urosepsis until the course of treatment of the infection has been completed and clinical recovery has occurred.

It is recommended that a follow-up urine culture be obtained within 7 days of clinical recovery from all urinary tract infections. Whether or not additional therapy is prescribed because of culture results should be determined by Investigator judgment, after consultation with the Medical Monitor.

It is the investigator's responsibility to report, as applicable based on Investigator's judgment and subject's medical history, related adverse events as defined in Section 6. Additional information, including but not limited to completion of supplemental eCRFs or questionnaires may be requested for certain adverse events and/or laboratory abnormalities which are reported/identified during the course of the study.

5.3.2.2 Guidance on Assessment of Hematuria

All events of hematuria (confirmed by microscopy) during the double blind phase of the study should be investigated according to local standards and best clinical practices for a possible cause. If an immediate or benign common cause is identified eg., menstruation, urinary tract infection (UTI) the cause should be treated and resolution be confirmed and documented with a microscopic urinary analysis (performed by central laboratory) at an unscheduled visit while the patient continues in the study (See appendix 3).

If **NO** common cause is identified, if a malignancy is otherwise suspected or positive hematuria (by microscopy) at the unscheduled repeat visit is found this should be captured on the nonserious AE CRF page or SAE page, as appropriate, (See section 6.3) and the supplemental hematuria CRF page, and patients should be further investigated based on American Urological Association (AUA) guidelines or equivalent local standard of care and best practices which could include referral to an urologist and undergoing evaluation that may include abdominal computed tomography (CT), urine cytology, and NMP-22 urine test. The patient should continue to receive investigational product treatment during these investigations (unless otherwise contraindicated).

It is the investigator's responsibility to report, as applicable based on Investigator's judgment and subject's medical history, related adverse events as defined in Section 6. Additional information, including but not limited to completion of supplemental eCRFs or questionnaires may be requested for certain adverse events and/or laboratory abnormalities which are reported/identified during the course of the study.

